2.0 OBJECTIVES AND ENDPOINTS

| Objectives | Endpoints | Justification for Endpoints |
|--|---|--|
| Primary | | |
| 
To determine the ctDNA clearance rate in patients with stage II melanoma who test positive for circulating tumor DNA and are treated with atezolizumab and tiragolumab.
 | 
ctDNA clearance rate, defined as the proportion of ctDNA-positive patients having a ctDNA-negative test at C3D1.
 | 
Immune checkpoint blockade (ICB) provides clinical benefit to a subset of patients with cancer. However, existing biomarkers do not reliably predict treatment response across diverse cancer types. Bratman et al showed how serial circulating tumor DNA (ctDNA) testing may perform as a predictive biomarker in patients receiving ICB. Authors ran a prospective phase II clinical trial to assess ctDNA in five distinct cohorts of patients (including melanoma) with advanced solid tumors treated with pembrolizumab (NCT02644369). They applied bespoke ctDNA assays to 316 serial plasma samples obtained at baseline and every three cycles from 94 patients. Baseline ctDNA concentration correlated with progression-free survival, overall survival, clinical response and clinical benefit. This association became stronger when considering ctDNA kinetics during treatment. All 12 patients with ctDNA clearance during treatment were alive
 |

| | | |
|---|--|---|
| | | with median 25 months follow up. This study demonstrates the potential for broad clinical utility of ctDNA-based surveillance in patients treated with ICB. ²² |
| Secondary | | |
| To determine the confirmed ctDNA negativity proportion with two consecutive negative results in patients with stage II melanoma who test positive for circulating tumor DNA and are treated with atezolizumab and tiragolumab, and those who are treated with atezolizumab alone. | Proportion of ctDNA-positive patients having a ctDNA-negative test at two consecutive measures | |

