| To determine the relapse-free survival in patients with stage II melanoma who test positive for circulating tumor DNA and are treated with atezolizumab and tiragolumab, and those who are treated with atezolizumab alone | Relapse-free survival (RFS), defined as the duration of time from the date of randomization to the date of earliest disease relapse or death, whichever occurs first. | RFS is an acceptable measure of clinical benefit for a late stage study that demonstrates superiority of a new antineoplastic therapy, especially if the magnitude of the effect is large and the therapy has an acceptable risk/benefit profile. |
| To determine the distant metastasis-free survival in patients with stage II melanoma who test positive for circulating tumor DNA and are treated with atezolizumab and tiragolumab, and those who are treated with atezolizumab alone (both circulating tumor DNA positive and negative). | Distant-metastasis free survival (DMFS), defined as the duration of time from the date of positive ctDNA being confirmed to the date of appearance of a distant metastasis or death, whichever occurs first. | The secondary efficacy objective of this study is to compare DMFS between the two treatment arms |
| To determine the overall survival of patients with stage II melanoma. | Overall survival (OS), defined as the duration of time from the date of positive ctDNA being confirmed to death from any cause. | The secondary efficacy objective of this study is to compare OS between the two treatment arms |
| To evaluate the safety and tolerability of atezolizumab | Defined as the number of treatment-related grade 3 or | Safety parameters commonly used for |

| | | |
|--|--|--|
| and tiragolumab in patients with stage II melanoma. | greater AEs and discontinuations due to treatment-related AEs. | evaluating investigational systemic anticancer treatments are included as safety endpoints including, but not limited to, the incidence of, causality, and outcome of AEs/serious adverse events (SAEs); and changes in vital signs and laboratory values. Adverse events will be assessed as defined by CTCAE, Version 5.0. |
| To assess the impact of ctDNA kinetics on outcomes (relapse-free survival, distant metastasis-free survival, and overall survival) in patients with surgically resected stage II melanoma. | | |

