4.5 Measures to Minimize Bias: Randomization

After enrollment to stage 1, patients who are determined to be ctDNA positive will be randomized to receive either atezolizumab and tiragolumab (treatment group) or atezolizumab monotherapy (reference group) on a 1:1 basis. The study will use a simple

randomization method. This method is equivalent to tossing a coin (where the probability of a head is 0.5) to determine treatment assignment (i.e., heads - atezolizumab and tiragolumab, tails – atezolizumab). Using the computer, a sequence of random numbers will be generated which are uniformly distributed between 0 and 1 and independent of each other. For the i-th patient entering the trial, if the i-th random number ≤ 0.5 , a combined treatment of atezolizumab and tiragolumab will be assigned; if the i-th random number > 0.5 then atezolizumab monotherapy will be assigned.

If it is determined (after analysis of stage 1) that enrollment will continue to stage 2, randomization will discontinue. All stage 2 patients will receive atezolizumab + tiragolumab.

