14.0 STATISTICAL CONSIDERATIONS

14.1 Study Design

This is an open-label, multi-center, Simon two-stage phase II study consisting of random allocation of a portion of patients to a small reference arm to offer some protection against the uncertainties and potential biases of a one-armed study while retaining some of the statistical efficiency. The reference arm is not a control group in the traditional sense and there will not be a formal efficacy comparison between the treatment and reference groups (Herson and Carter, 1986; Rubinstein, et. al., 2009).

The purpose of this study is to evaluate the efficacy and safety of atezolizumab and tiragolumab in stage II melanoma patients who had undergone complete resection and been tested positive for circulating tumor DNA (ctDNA). In this study, the treatment arm (i.e., atezolizumab and tiragolumab) will not be compared with the reference arm (i.e., atezolizumab only); it will be analyzed against historical control as a one-armed study. The reference arm is intended to only act as a check on the similarity of the current patients to the historical control for a descriptive estimation of ctDNA clearance.

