14.7 Statistical Analyses

Descriptive statistics will be used to summarize the trial results. Statistics for continuous variables may include means, medians, ranges and appropriate measures of variability. Qualitative variables will be summarized by counts and percentages. The uncertainty of estimates will be assessed by confidence intervals (CIs). All analyses will be considered as exploratory, even if statistical tests will be used.

ctDNA clearance and confirmed negative rate, as well as safety data will be summarized by the number and proportions. RFS, DMFS, and OS will be presented via the Kaplan-Meier method. Median survival and corresponding two-sided 95% CIs will be computed. Survival rates with 95% CIs will be estimated. The group survival difference (i.e., treatment vs. reference) will be examined by the log-rank test. Further exploratory correlative analyses will be performed via Fisher exact test, t-test, or nonparametric Wilcoxon–Mann–Whitney test, if needed.

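### The between-arm survival comparison is an unadjusted log-rank test, not confined to the randomised patients, that makes no use of baseline ctDNA level

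*Combined protocol and SAP*

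**What the plan says.** **Analysis.** Section 14.7 plans Kaplan-Meier curves for RFS, DMFS and OS, and then: "The group survival difference (i.e., treatment vs. reference) will be examined by the log-rank test". The only other tests listed are in this sentence: "Further exploratory correlative analyses will be performed via Fisher exact test, t-test, or nonparametric Wilcoxon–Mann–Whitney test, if needed". No hazard ratio or regression model is planned.

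**Allocation.** Section 4.5 uses simple randomisation in stage 1, without blocks or strata: "This method is equivalent to tossing a coin (where the probability of a head is 0.5) to determine treatment assignment". Section 14.5 randomises 36 patients. If stage 2 opens, 25 more receive the combination without randomisation, so Section 14.6 has 43 combination and 18 reference patients.

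**Baseline ctDNA.** A positive test is required for treatment (3.2.1), the sample is drawn at Step 2 screening (9.3), and a baseline ctDNA form exists (10.0). Section 9.3 intends to follow titres and relate changes in level to outcome. On prognosis, the endpoint justification in Section 2.0 reports from a cited pembrolizumab study: "Baseline ctDNA concentration correlated with progression-free survival, overall survival, clinical response and clinical benefit". Section 1.2 makes a similar remark about the amount of ctDNA in a late-stage BRAF-mutant cohort.

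**Status of the comparison.** Section 14.1 says that "there will not be a formal efficacy comparison between the treatment and reference groups", and 14.7 adds: "All analyses will be considered as exploratory, even if statistical tests will be used". Against that, the objectives table in 2.0 says: "The secondary efficacy objective of this study is to compare DMFS between the two treatment arms". It says the same for OS.

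**The concern.** There are two weaknesses.

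First, the population of the log-rank test is not defined. If stage 2 opens and all treated patients are used, more than half of the combination arm (25 of 43) was enrolled later and without randomisation. A difference in patient mix between the stages could then appear as a treatment difference.

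Second, even within the 36 randomised patients nothing in the design or the analysis protects against imbalance in baseline ctDNA level. At about 18 per arm such an imbalance is common. If the level is prognostic, it can noticeably distort the only randomised evidence on clinical outcome in the trial. A pre-specified covariate would deal with this. The same adjustment added after outcomes are known would look data-driven.

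**Working it through.** **1. The plan's own figures.** With r1/n1 = 2/18 and r/n = 7/43, P(promising | p) = Σ(x=3..18) b(x; 18, p) · P(Y ≥ 8 − x), with Y ~ Bin(25, p). This gives 0.0480 at p = 0.10 and 0.8003 at p = 0.25, as Section 14.5 states. Screening is 36/0.25 = 144 plus 25/0.25 = 100, total 244. The primary design reproduces and this point does not touch it. The plan gives no effect size, event count or power for the log-rank test, so everything below rests on assumptions.

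**2. How likely imbalance is.**
- A coin toss over 36 patients gives exactly 18/18 with probability 13.2%, and 22/14 or more uneven with probability 24.3%.
- Even at 18/18, a split of 11 v 7 or worse in patients above the median ctDNA level has probability 31.8%.
- The SD of the between-arm difference in mean log ctDNA is √(2/18) = 0.33 covariate SD. A one-SD imbalance multiplies the observed hazard ratio by about HRx^0.333, where HRx is the ctDNA hazard ratio per SD: 1.14 at 1.5, 1.26 at 2, 1.36 at 2.5.

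**3. RFS power in the randomised patients.** Assumptions: 18 v 18, exponential times, hazard 0.69 per year, censoring at 2.7 years, about 25 events, true HR 0.5, two-sided 5%, 3,000 trials per setting. Ranges are over repeated runs.

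| ctDNA HR per SD | Log-rank | Cox with log ctDNA |
|---|---|---|
| 1.25 | 0.42 | 0.42 |
| 1.5 | 0.37 | 0.40 |
| 2 | 0.28-0.30 | 0.38-0.40 |
| 2.5 | 0.26 | 0.36-0.38 |

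A second set-up (coin-toss allocation, about 65% events, 4,000 trials) used a true HR of 0.57, borrowed from the lung-cancer PFS result in Section 1.5. Power went from 21.0% to 21.2%, from 18.8% to 22.2% and from 15.3% to 23.0% at ctDNA HR 1.5, 2 and 3. Type I error was 5.0-5.3% unadjusted and 5.0% adjusted. By Schoenfeld's formula, 80% power at HR 0.57 needs 4(1.96 + 0.842)²/(ln 0.57)² ≈ 100 events, more than 36 patients can supply.

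**4. The estimate under imbalance.** In the second set-up, these are median estimates of a true HR of 0.57, over all trials and over those where the combination arm starts more than 1/3 SD higher:

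| ctDNA HR per SD | Unadjusted, all trials | Unadjusted, imbalanced | Adjusted, imbalanced |
|---|---|---|---|
| 1.5 | 0.58 | 0.70 | 0.56 |
| 2 | 0.62 | 0.85 | 0.57 |
| 3 | 0.66 | 0.98 | 0.54 |

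The step from the first column to the second is the effect of imbalance: 0.70/0.58 = 1.21, 0.85/0.62 = 1.37 and 0.98/0.66 = 1.48.

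**5. Non-randomised stage 2 patients.** For 43 v 18 with no drug effect, suppose the 25 stage 2 patients have log ctDNA 0.5 to 1 SD lower. The unadjusted log-rank test then rejects in 7-12%, 8-17% and 11-25% of trials at ctDNA HR 1.5, 2 and 3. The adjusted model rejects in about 4-6%. With no shift the unadjusted test rejects in about 5-6%.

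**6. Few events.** With about 7 to 8 events (assumed hazard 0.1 per year), log-rank power was 0.12-0.15 and the adjusted Cox Wald test 0.03-0.10. Few deaths are plausible, because patients who stop treatment for recurrence leave the study after the 90-day adverse-event follow-up (5.6, 5.7).

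**The case against.** The strongest reply is that nothing here is an error. The log-rank test is valid under randomisation, 14.1 and 14.6 give the reference arm a descriptive role, and 14.7 calls every analysis exploratory. All of that stands. It does not remove the point, because 14.7 still specifies the test and 2.0 still lists comparing DMFS and OS between arms as an objective.

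Four stronger readings are tempting, and the documents do not support them.
- *The protocol says level is prognostic in these patients.* The statements on level come from advanced or late-stage disease. The resected stage II/III evidence in 1.2 concerns detectable against undetectable ctDNA, and here everyone is positive. No prognostic strength is given for this population.
- *The value is already in hand.* The draw is certain and 9.3 implies a quantity, but 1.3 describes the laboratory report as showing presence or absence, and 10.0 does not list the fields of the ctDNA form.
- *The unadjusted analysis is biased toward no effect.* An average unadjusted hazard ratio nearer 1 reflects non-collapsibility: marginal and conditional hazard ratios are different quantities.
- *Adjustment is better for all three endpoints.* With very few events the adjusted Wald test does worse than the log-rank test. Part of that comes from the Wald form itself, but it rules out making the adjusted model the lead analysis for OS.

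**Conclusion.** The point holds as a modest improvement to an exploratory secondary analysis. The unadjusted test keeps its error rate in the randomised patients. What it gives up depends on an unknown, the prognostic strength of ctDNA level among ctDNA-positive resected stage II patients. At an assumed hazard ratio of 2 to 2.5 per SD, adjustment adds about 10 points of RFS power (0.26-0.30 to 0.36-0.40 at a true HR of 0.5) and keeps the estimate stable when the arms start unequal. At 1.5 or below the power gain is 0 to 3 points. The comparison is underpowered either way.

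The undefined population is the firmer part of the point, since it follows from the text alone: 14.7 does not keep the 25 non-randomised patients out of the test. How much that matters depends on whether patient mix shifts between stages. The documents neither show nor exclude such a shift.

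A reader might infer that the trial's go/no-go decision is at risk. It is not: that decision is single-arm, against a fixed 10% clearance rate.

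**What to change.** Add to Section 14.7:

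> The between-arm comparison of RFS, DMFS and OS is restricted to the randomised stage 1 patients; any 43 v 18 display is labelled non-randomised. For RFS, a Cox model with treatment and log-transformed Step 2 ctDNA level gives the adjusted hazard ratio with 95% CI, reported with the log-rank test. For DMFS and OS the log-rank test stays the main analysis, and the adjusted model is reported only if events are sufficient.

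State in advance what number of events counts as sufficient. Record the quantitative Step 2 value on the baseline ctDNA form, and confirm with the laboratory that it is reported. If only presence or absence is available, the covariate part cannot be done, but the restriction to randomised patients still applies. Sections 2.0, 14.1 and 14.7 should also agree on whether the arms are compared.

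Cost: a few lines of SAP text, one extra model and possibly one form field. The adjusted hazard ratio is conditional on ctDNA level rather than marginal, and the report should say so. No change to sample size, randomisation or the primary analysis.

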| Treatment consent | | X | | | | |
| Review of medical record | X | | | | | |
| Confirmation of resection | X | | | | | |
| H&P, PS, wt | | X | X | | X | |
| CBC | | X | X | | | |
| CMP, LDH, amylase, lipase | | X | X | | | |
| TSH, free T3 or total T3, free T4 | | X | X | | | |
| INR, aPTT ⁹ | | X | | | | |
| EBV serology | X ¹¹ | | | | | |
| HIV serology | X ¹¹ | | | | | |
| HBV serology | X ¹¹ | | | | | |
| HCV serology | X ¹¹ | | | | | |
| Pregnancy test ³ | | X | X | | | |
| Urinalysis reflex to micro and/or culture ⁹ | | X | | | | |
| ECG | | X | X ¹² | | | |
| Randomization ⁶ | | X | | | | |
| Blood for ctDNA (Signatera testing) | | X ⁵ | X ⁸ | | X ¹⁰ | |
| Whole blood and tissue for whole exome sequencing (for design of Signatera assay) | X ¹³ | | | | | |
| Atezolizumab | | | X ⁴ | | | |
| Tiragolumab ⁷ | | | X ⁴ | | | |
| CT scan | | X | | X ² | | X |
| AE assessment | | | Baseline through 90 days after last day of treatment | | | |

1. corresponds with the end of every 3rd cycle; if there are treatment delays, imaging should continue to be done every 12 weeks rather than waiting for the end of every 3rd cycle

2. Q12W during Years 1 and 2 after surgery, Q24W during Year 3 after surgery; depending on when a patient discontinues treatment, follow-up may be Q12W or Q24W; follow-up will discontinue after 3 years have elapsed from date of surgery

3. women of childbearing potential only

4. treatment can continue for up to 13 cycles; refer to Section 5.2 for instructions regarding monitoring of vital signs and post-infusion observation

5. must take place 4-12 weeks after surgery; if ctDNA positive, patients will be randomized to receive either atezolizumab and tiragolumab or atezolizumab monotherapy, and if ctDNA negative, patient will not continue in this study

6. stage 1 only; randomization must occur no more than 16 weeks after date of surgery

7. if randomized to receive tiragolumab during stage 1; all patients during stage 2.

8. prior to dosing on C3D1, C6D1, C9D1, C12D1 – the collection of blood for ctDNA should be discontinued after 2 consecutive negative tests

9. required at Step 2 screening and thereafter only as clinically indicated

10. optional

11. may take place up to 42 days prior to C1D1
12. ECG should be performed at Step 2 screening, C3D1, C6D1, C9D1, and C12D1

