9.3 Blood for ctDNA

Twenty mL of peripheral blood will be drawn into 2 pre-labeled circulating tumor DNA BCT tubes (Streck 218962, NAT-800632) at the following time points:

- Step 2 screening (4 to 12 weeks after date of surgery)
- C3D1
- C6D1
- C9D1
- C12D1
- End of treatment (OPTIONAL)

We will follow ctDNA titers longitudinally and correlate level changes with treatment response and/or relapse based on clinical and/or radiographical assessments. Note that ctDNA testing will be discontinued after two consecutive negative tests.

Immediately after blood is drawn, thoroughly mix the blood with the anticoagulant by gently inverting it 8 times. Do not shake vigorously.

Tubes should be shipped to Natera at ambient temperature within 24 hours of collection.

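### The ctDNA-kinetics objective has no suitable time-to-event method, and grouping patients by confirmed or later clearance from time zero would favour clearers even if clearance has no effect

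*Combined protocol and SAP*

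**What the plan says.** Section 2.0 and the Protocol Summary list a secondary objective: "To assess the impact of ctDNA kinetics on outcomes (relapse-free survival, distant metastasis-free survival, and overall survival"). Its endpoint cell in Section 2.0 is empty, and no kinetics variable is defined elsewhere. Section 9.3 adds: "We will follow ctDNA titers longitudinally and correlate level changes with treatment response and/or relapse based on clinical and/or radiographical assessments".

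Section 14.7 has three relevant statements:
- Estimation: "RFS, DMFS, and OS will be presented via the Kaplan-Meier method". This is not linked to ctDNA groups.
- Testing: "The group survival difference (i.e., treatment vs. reference) will be examined by the log-rank test".
- Correlative work: "Further exploratory correlative analyses will be performed via Fisher exact test, t-test, or nonparametric Wilcoxon"–Mann–Whitney, with the rider that this is done if needed.

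It names no landmark, no Cox model and no time-dependent covariate. It also states: "All analyses will be considered as exploratory, even if statistical tests will be used".

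On timing, the Schedule of Activities places the on-treatment draws "prior to dosing on C3D1, C6D1, C9D1, C12D1". Section 14.3 starts RFS, DMFS and OS at confirmed ctDNA positivity, while Sections 2.0 and 11.0 start RFS at randomization. Either origin comes before the first on-treatment test. Under Sections 5.6 and 5.7, patients who stop treatment for recurrence go off study once the 90-day adverse-event follow-up is complete.

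**The concern.** The outcomes in this objective are censored times, and the exposure is a test result obtained during follow-up. The plan as written covers neither feature.

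Fisher's test on event yes/no ignores when events occur and how long each patient was followed. The t-test and Wilcoxon test on raw follow-up time treat censored times as events.

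The second feature matters more. To be called confirmed negative, or cleared at a later visit, a patient must still be on study and in practice relapse-free at that visit. Patients who relapse early can only fall in the other group. If time is counted from before the visit, the negative group carries event-free time that its members had to have. A relation between ctDNA response and outcome would then appear without any effect of clearance, and could later be quoted as support for ctDNA clearance as an endpoint in this disease.

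**Working it through.** **1. The plan's own figures.** No figure is stated for the kinetics analysis. The ctDNA design figures are those of the two-stage rule in Section 14.5 (18 + 25 patients; continue if at least 3 clear; promising if at least 8 of 43). With b the binomial probability,

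P(promising | p) = Σ over x = 3…18 of b(x; 18, p) × P(Bin(25, p) ≥ 8 − x).

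At p = 0.10 this is 0.0480 and at p = 0.25 it is 0.8003, so the stated alpha of 0.05 and power of 0.8 reproduce. Nothing in the rule uses the kinetics analysis.

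**2. When each patient can be classified.** Cycles last 28 days, so cycle k starts 4 × (k − 1) weeks after C1D1. C3D1, C6D1, C9D1 and C12D1 fall at weeks 8, 20, 32 and 44. Two consecutive on-treatment negatives cannot exist before week 20.

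**3. The guaranteed time, by hand.** Assume exponential RFS with a median of 52 weeks, so S(t) = 0.5^(t/52). Section 1.2 reports that most ctDNA-positive patients relapsed within a year of surgery, which makes this median plausible but does not fix it. Of the 61 patients to be treated:
- Relapsed before week 20: 61 × (1 − 0.5^(20/52)) = 61 × 0.234 ≈ 14. If relapse is found only at 12-weekly scans, those found by then are the week-12 ones: 61 × (1 − 0.5^(12/52)) = 61 × 0.148 ≈ 9.
- Relapsed before week 8: 61 × (1 − 0.5^(8/52)) = 61 × 0.101 ≈ 6. With scan-only detection this is 0, because the first on-treatment scan falls at week 12.

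So 9 to 14 of the earliest relapses must land in the not-confirmed group, whatever clearance does.

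**4. Simulation with no true effect.** Clearance is independent of relapse, with probability 25% at C3D1 and 10% at each later test. N = 61 and median RFS is 12 months. Entries are the share of trials falsely significant in favour of confirmed-negative patients, with time counted from zero (nominal 2.5%).

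| Test | Relapse found only at 12-weekly scans | Relapse detected continuously |
|---|---|---|
| Log-rank | 24% | 37% |
| Wilcoxon on follow-up time | 45% | 67% |
| Fisher on event yes/no | 8% | 13% |

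Repeating the calculation with other follow-up horizons gave the same picture, with the continuous-detection log-rank and Fisher figures moving by a few percentage points.

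**5. Sensitivity for confirmed negativity.** With 25% clearing at every test, persistent once cleared, and continuous detection: log-rank 73%, Wilcoxon 95%, Fisher 18%, event-rate ratio 0.49. With results independent from test to test: 10%, 24%, 7% and 0.66. Over medians of 26 to 104 weeks and both clearing models, Wilcoxon runs from 12% to 100%, Fisher from 3% to 21%, and the rate ratio from 0.41 to 0.70.

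**6. The protocol's own C3D1 clearance** (25% at every test, persistent, median 52 weeks, N = 61, continuous detection):
- Patients with a C3D1 sample only: events 84% in both groups, rate ratio 1.00, false positives 1.5–2.0%. No bias.
- Patients without a sample counted as not cleared: rate ratio 0.86, Wilcoxon 8.9%, log-rank 4.1%, Fisher 3.3%. With scan-only detection the ratio is 1.01 and the bias disappears.

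**7. With a landmark.** Restricting to patients event-free at C6D1 and counting time from there returns false positives to about 2% in the step 4 setting. In the step 6 setting the rate ratio is 1.01.

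**The case against.** Five points can be made for the plan.

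- **The protocol defines clearance at C3D1, and Section 5.3 requires a C3D1 sample.** Both groups have then reached C3D1. This stands. A reader might infer that clearers will look better however the analysis is done; the documents do not support that. The bias applies to confirmed negativity, later clearance and serial level changes. It can return in modest form at C3D1 if unsampled patients count as not cleared, which Section 5.3 leaves open for stage 2 patients, who are not replaced.
- **Censoring is not the root cause.** This also stands. A log-rank test handles censoring and is still biased from time zero, so replacing the named tests with a survival test would not be enough.
- **The plan does not assign Fisher, t or Wilcoxon tests to this objective.** They are offered if needed. Correct: it is a gap, not a stated wrong analysis. But no other method is named for the objective.
- **The inputs are assumed.** The median, the clearing probabilities and the mode of relapse detection are not document figures, and the background cohort was stage II/III timed from surgery. The size is therefore uncertain. The direction is the same in every scenario tried.
- **Everything is labelled exploratory.** That lowers the importance, but the label does not remove bias from a reported association.

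It is also tempting to say that the trial's case for its primary endpoint depends on this analysis. It does not: Section 2.0 justifies the endpoint from an external pembrolizumab study, and the rules in Section 14.5 use only C3D1 counts.

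**Conclusion.** The point holds in limited form. A secondary objective on three censored outcomes has no defined exposure variable and no suitable method in Section 14.7. If patients are grouped by confirmed negativity or later clearance and timed from confirmed positivity or randomization, a spurious benefit is likely: roughly ten to fifteen times the nominal 2.5% for log-rank (24/2.5 ≈ 10; 37/2.5 ≈ 15) under the main assumptions, more for Wilcoxon and less for Fisher. These figures rest on an assumed 12-month median RFS, 25% then 10% clearing per test and 61 patients. C3D1 clearance among sampled patients is free of this bias. This is a cheap improvement to an exploratory secondary analysis and leaves the primary result untouched.

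**What to change.** Amend Section 14.7, and fill the empty endpoint cell in Section 2.0, to state:

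- **The variables:** C3D1 clearance, confirmed negativity and, if wanted, a named measure of level change.
- **Landmark analyses:** C3D1 for clearance and C6D1 for confirmed negativity. Include patients event-free and sampled at the landmark, group them by results known at that date, count time from it, and use Kaplan-Meier and Cox.
- **Later clearance:** a time-dependent Cox covariate that changes on the date of the qualifying test. Because draws stop after two consecutive negatives, say how status is carried forward.
- **Missing C3D1 samples:** how such patients are handled in this analysis.
- **Exclusion:** no Fisher, t or Wilcoxon tests for RFS, DMFS or OS.

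The cost is SAP wording and a little more analysis, with no new visits, samples or patients. Patients with an event before the landmark leave that analysis: under the assumed median, 0 to 6 of 61 at C3D1 and about 9 to 14 at C6D1, with some loss of precision. The time-dependent model keeps them. Neither method makes up for DMFS and OS follow-up that ends at recurrence, so results for those two outcomes should be reported with that limit stated.
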